7.3.4 Subject Compliance Monitoring

Insert the procedures for monitoring subject compliance.

Participants will receive one week of study intervention at a time, provided by Penn State Research Pharmacy. Medication will be delivered weekly to the Milton S. Hershey Medical Center Adolescent Medicine and Eating Disorders Clinic. At the time of delivery of a new week's supply of medication, participants will return any unused medication for pill counts to determine adherence.

Additionally, participants in PHP are allowed to either self-administer medication or receive medication from their parents, if under 18 years of age. Participants will have the option to take medication on-site during programming, either as self-administration if over 18 years of age or from a parent if 17 years of age or younger, as they will be in clinic for about 8 hours a day, from their own supply. No study or clinic staff will handle medication. No study or clinic staff will administer medication.

7.3.5 Blinding of the Test Article

Describe how the test article is blinded.

The Penn State Health IDS pharmacy will purchase Naltrexone 50mg tablets from a pharmaceutical wholesaler. The IDS pharmacy will purchase gelatin capsules and USP grade methylcellulose from a pharmacy supplier to be used for compounding the active and placebo capsules. For the active Naltrexone 50mg capsules, a Naltrexone 50mg tablet will be placed in an empty gelatin capsule with methylcellulose filler. The placebo capsules will be empty gelatin capsules filled with Methylcellulose.

7.3.6 Receiving, Storage, Dispensing and Return

7.3.6.1 Receipt of Test Article

Describe how the test article will be obtained and from what source. Describe how the study test article will be packaged along with amounts (e.g., number of tablets/capsules or volume of liquid) and labeling. If drug kits are used, describe all the contents of the kit and associated labeling.

The Penn State Health IDS pharmacy will purchase Naltrexone 50mg tablets from a pharmaceutical wholesaler. The IDS pharmacy will purchase gelatin capsules and USP grade methylcellulose from a pharmacy supplier to be used for compounding the active and placebo capsules. For the active Naltrexone 50mg capsules, a Naltrexone 50mg tablet will be placed in an empty gelatin capsule with methylcellulose filler. The placebo capsules will be empty gelatin capsules filled with Methylcellulose.

Participants will receive seven gelatin capsules at a time, packaged in conventional amber plastic medication bottles with child safety caps. These will be brought to the Milton S. Hershey Medical Center Adolescent Medicine and Eating Disorders Clinic weekly by Penn State Research Pharmacy staff and given to participants in that setting. At time of receipt of one week's worth of study medication, any remaining medication from the previous week will be returned to the research pharmacy and disposed of by pharmacy staff according to guidelines.

7.3.6.2 Storage

Describe the plans to store, handle the test article so they will be used only on subjects and only by authorized investigators. Describe storage temperature requirements and how temperature will be monitored and recorded.

As described above, test article will be dispensed to participants or participants' parents/legal guardians in the MSHMC Adolescent Medicine and Eating Disorders Clinic. All participants in this study are also patients in PHP, therefore they all have patient identification bands while they are onside. Participant identity will be verified with ID bands, and their legal guardians will be identified by government-issued photo identification. Participants can self-administer test-article on site during PHP, or participants' parents can administer the test article on site. While this is clearly optional and not feasible for all participants on all days—especially weekends—this method will be encouraged by study staff, though study and clinic staff will neither handle nor administer study medication.

Oral naltrexone tablets are stable at room temperature, between 20-25 degrees centigrade⁷. No specific temperature monitoring is necessary.

7.3.6.3 Preparation and Dispensing

Describe how the test article will be assigned to each subject and dispensed. Describe the steps necessary to prepare the test article. Include where the test article preparation will be done and by whom. Fully describe how the study treatment is to be administered and by whom.

Subjects will be randomly assigned to study article or to placebo as described above. The IDS pharmacy will purchase gelatin capsules and USP grade methylcellulose from a pharmacy supplier to be used for compounding the active and placebo capsules. For the active Naltrexone 50mg capsules, a Naltrexone 50mg tablet will be placed in an empty gelatin capsule with methylcellulose filler. The placebo capsules will be empty gelatin capsules filled with Methylcellulose.

The study article or placebo will be self-administered as an oral medication.

7.3.6.4 Return or Destruction of the Test Article

Describe the procedures for final reconciliation of the test article supply at the end of the study and whether the test article is to be shipped back to a source or destroyed on site.

Expired medications and medications returned by subjects unused will be documented and destroyed as per the IDS Destruction Policy. At the end of the study, any remaining study medications will be documented and destroyed as per the IDS Destruction Policy.

7.3.6.5 Prior and Concomitant Therapy

Describe what prior and/or concomitant medical therapy will be collected. Describe which concomitant medicines/therapies are permitted during the study. Describe which concomitant medicines are not permitted during the study.

Many patients in PHP are on other medications, some of which are relevant to psychiatric diagnoses—such as selective serotonin reuptake inhibitors—and several are not, such as polyethylene glycol for constipation. Medication usage will be tracked during this study by following medication reconciliation performed at biweekly medical appointments while in PHP, which is the standard of care for patients requiring this level of care.

Participants will be permitted any medication other than opioid medications. Any potential participant with a prescription for opioid medication, such as buprenorphine/naloxone combination strips or with a positive urine drug screen for opioids will be excluded. Any participant requiring opioid painkillers during this study will be dropped from the protocol. Patients will not be permitted to use medical cannabis during this study.

8.0 Subject Numbers and Statistical Plan

8.1 Number of Subjects

Indicate the maximum number of subjects to be accrued/enrolled. Distinguish between the number of subjects who are expected to be enrolled and screened, and the number of subjects needed to complete the research procedures if applicable (i.e., numbers of subjects excluding screen failures.)

Because this is a pilot study, we have decided *a priori* to enroll 30 participants in each arm of treatment for a total of sixty subjects. In 2019, approximately 150 patients meeting criteria for potential inclusion (between ages of 12-18, needing PHP level of care in the eating disorder clinic, no diagnosis of gender dysphoria or intellectual disability, with diagnoses of anorexia nervosa, or bulimia nervosa) were seen for initial evaluation in the eating disorder clinic. Therefore we hope to be able to enroll sixty participants over the course of 12 to 18 months.

8.2 Sample size determination

If applicable, provide a justification of the sample size outlined in section 8.1 to include reflections on, or calculations of, the power of the study.

This is a pilot study, and enrollment size was determined *a priori* to allow for completion of enrollment within 18 months.

8.3 Statistical methods

Describe the statistical methods (or non-statistical methods of analysis) that will be employed.

For analysis, data will be analyzed for differences between participants receiving naltrexone and participants receiving placebo. The data will be analyzed for demography differences between the two groups at baseline, and outcomes will be compared at three and six weeks; as well as at 6 months. Outcomes to be compared are stated in section 1.1 and 1.2. Within each group, these outcomes will also be compared across time. Statistically significant differences between each group at each endpoint will be noted and reported.

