1.1 Study Objectives

Describe the purpose, specific aims or objectives. State the hypotheses to be tested.

The objective of this study is to evaluate the effectiveness of oral naltrexone tablets in pediatric and adolescent eating disorders, in particular anorexia nervosa and bulimia nervosa, as compared to placebo. The hypothesis of this study is that patients receiving oral naltrexone will demonstrate greater improvement in their score on the ED-15, an evidence-based metric of eating disorder symptom severity and frequency¹, than those receiving placebo, representing more complete recovery from eating disorder

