1.2 Primary Study Endpoints

State the primary endpoints to be measured in the study.

Clinical trials typically have a primary objective or endpoint. Additional objectives and endpoints are secondary. The endpoints (or outcomes), determined for each study subject, are the quantitative measurements required by the objectives. Measuring the selected endpoints is the goal of a trial (examples: response rate and survival).

The primary outcome will be clinically and statistically significant reduction in ED-15 score in those receiving medication vs placebo.

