7.1 Study Design

Describe and explain the study design.

This is a double-blind, randomized, placebo-controlled study. We have developed the following schedule of events. All events with a superscript $^{\circ}$ are for study purposes only and are not part of the standard of care:

	Pre-Enrollment Screening: Medical	Enrollment	Week 1	Week 2	Week 3	Week 4	Week 5	Week 6 (end of treatment	Week 8-9 (post- treatment)	Six Months
Intervention								_	>	
Initial Medical Assessment	Х									
Subsequent Medical Assessment, including comprehensive review of systems			x		x		x		х	х
Initial Psychiatry Assessment	X									
Subsequent Psychiatric Assessment, including suicidal ideation			х	х	х	х	х	х	х	х
Discussion of risks and benefits, inclusion and exclusion criteria ^o		х								
Consent/Assent ^o		Х								
\$25 Greenphire Clincardo		Х								х
Urine Drug Screen ^o		Х								
Serum Pregnancy Test (female participants)°		х								
Urine Pregnancy Test (female participants)°					х			х		
Administer Study Article ^o			Х	Х	х	Х	Х	х		
EKG	X									
AST	X				Xº			Xº		
ALT	Х				χ°			Xo		
Total Bilirubin	Х				Xº			Xº		
Direct bilirubin	Х				Xº			Xº		
Heart Rate	Х		Х	Х	Х	Х	Х	Х	Х	Х
BMI	X		Х	Х	Х	Х	Х	X	Х	Х
Height	X		Х	X	X	X	Х	X	X	Х
Weight	X		X	X	X	X	X	X	X	X
Blood Pressure	X		X	X	X	X	X	X	X	X
Temperature Adverse event monitoring ^o	Х		X	x	x	x	x	x	X	X
Suicidal Ideation Screening (ASQ			^	^	^	^	^			
for age <17or C-SSRS for age 18+)		х	Х	Х	х	Х	Х	х	Х	Х
ED-15		Х	х		х			Х	X	х
EDE-Q		Х	х		х			Х	X	Х
ABUSI°		Х	Х		х			Х	Х	Х
GAD-7		Х	х		х			Х	Х	Х
PHQ-9		Х	Х		Х			Х	X	Х
BIS/BAS°		Х	Х		Х			Х	Х	Х

Note: Medical assessments may occur in weeks 1,3 etc or 2,4 etc depending on standard of care for that patient. As long as patients are seen within a 14 day interval (2 week timeframe), the exact week intervals (1,3 or 2,4) may vary. Additionally, the 6 month follow up appointment may take place any time between 5-7 months after study enrollment ends.

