7.3.3 Method for Assigning Subject to Treatment Groups

Describe the randomization process and how the associated treatment assignment will be made.

Subjects will be randomized at enrollment using RedCap. Randomization will be stratified by age (16 and under or 17 and older) and diagnosis (anorexia nervosa binge/purge subtype and bulimia nervosa or OSFED with bingeing or purging behaviors), equaling 4 strata.

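### Section 8.3 does not commit the between-arm ED-15 comparison to adjustment for enrollment ED-15 or the randomization strata, and so gives up precision the trial could have at almost no cost.

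*Combined protocol and SAP*

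**What the plan says.** Section 8.3 states that "data will be analyzed for differences between participants receiving naltrexone and participants receiving placebo" and that "outcomes will be compared at three and six weeks; as well as at 6 months". It names no model, test, covariate or stratification factor. Its only between-arm use of baseline data is a check for demographic differences. For the outcomes it points elsewhere: "Outcomes to be compared are stated in section 1.1 and 1.2".

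Section 1.1 hypothesizes "greater improvement in their score on the ED-15". Section 1.2 defines the primary outcome as a "clinically and statistically significant reduction in ED-15 score in those receiving medication vs placebo". Both phrases could be read as a change from baseline, but neither makes baseline a covariate.

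The variables needed for adjustment are already collected:

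- **Enrollment ED-15.** Section 7.1 introduces its table with "We have developed the following schedule of events", and the ED-15 row is marked in the Enrollment column. Section 7.2 (Study Procedures) has ED-15 as routine in the adult program and asks for it from child-program participants who join the study. Section 19.1.1 says enrollment scores are recorded in REDCap.
- **Strata.** Section 7.3.3 says "Randomization will be stratified by age (16 and under or 17 and older) and diagnosis", "equaling 4 strata". The levels must be known before a participant can be randomized.

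**The concern.** When the enrollment score predicts the follow-up score, comparing raw follow-up scores leaves explainable variation in the error term. A change score uses baseline, but with a fixed coefficient of 1, which adds noise when the correlation is modest. ANCOVA estimates the coefficient. In large samples its standard error is no larger than that of either alternative.

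Section 8.3 does not forbid adjustment, but nothing in it commits the trial to adjust. It leaves open whether follow-up, change or adjusted scores are compared, so that choice could be made after the data are seen.

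Precision is scarce here. Section 8.1 sets 30 per arm, section 3.3.1 removes participants who need a higher level of care, and section 3.3.2 says that withdrawn subjects need not be replaced. Section 1.2 nevertheless asks for a statistically significant difference from placebo.

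**Working it through.** **Inputs from the documents.** 30 per arm, 60 in total (8.1). Two age levels by two diagnosis levels (7.3.3). Section 8.2 sets the size on feasibility and gives no power calculation, so there is no planned figure to reproduce.

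**Assumptions, not in the documents.** Correlation r between enrollment and follow-up ED-15 of 0, 0.3, 0.5 or 0.7; equal SDs; true difference 0.5 SD; two-sided 5% alpha; strata of equal size.

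**Standard error by formula, relative to follow-up scores.** Follow-up 1; change √(2(1−r)); ANCOVA on baseline √(1−r²).

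- ANCOVA ÷ follow-up at r = 0.3, 0.5, 0.7: 0.954, 0.866, 0.714 (5%, 13%, 29% smaller).
- ANCOVA ÷ change: 0.806, 0.866, 0.922 (19%, 13%, 8% smaller).

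**Half-width of the 95% interval, in SD units.** Half-width = t(0.975, df) × √((2/n) × V). For ANCOVA with k covariates, V = (1−r²)(1 + k/(N−k−3)) and df = N−2−k.

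- Follow-up, n = 30: 2.002 × √(2/30) = 0.517.
- Baseline only (k = 1), r = 0.5: V = 0.75 × (1 + 1/56) = 0.763, half-width 0.452.
- Baseline, age and diagnosis (k = 3), r = 0.5: V = 0.75 × (1 + 3/54) = 0.792, half-width 0.460.

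**Simulation.** 20,000 trials per setting, strata with no effect on outcome, allocation not blocked within strata; Monte Carlo error about ±0.7 points of power.

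| r | Measure | Follow-up | Change | ANCOVA, baseline | ANCOVA, baseline + strata |
|---|---|---|---|---|---|
| 0 | Power % | 47.6 | 26.7 | 46.8 | 45.5 |
| 0.3 | Power % | 47.8 | 36.9 | 51.1 | 49.7 |
| 0.3 | Half-width | 0.515 | 0.608 | 0.495 | 0.505 |
| 0.5 | Power % | 47.8 | 48.3 | 59.1 | 57.7 |
| 0.5 | Half-width | 0.515 | 0.514 | 0.450 | 0.458 |
| 0.7 | Power % | 48.3 | 69.6 | 75.9 | 74.2 |
| 0.7 | Half-width | 0.515 | 0.398 | 0.371 | 0.378 |

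With all three covariates, the interval at r = 0.3, 0.5, 0.7 is narrower:

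- than for follow-up scores by 2%, 11%, 27% (for example, 1 − 0.458/0.515 = 11%);
- than for change scores by 17%, 11%, 5%.

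**Effect of the strata at r = 0.5.** If the strata act only through baseline, power with all covariates is 57%. If they predict outcome independently of baseline with R² of 0.1 or 0.2, it is 64% or 71%.

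**Dropout.** With an assumed 25 completers per arm and r = 0.5, power goes from 41% (follow-up) to 49%, and the half-width from 0.566 to 0.507.

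**Balanced strata.** Stratified randomization is meant to balance the arms within strata. When they are balanced, the half-width at r = 0.5 with baseline and strata is about 0.45, no wider than with baseline alone. Power at r = 0 is 46.8% adjusted against 47.8% unadjusted.

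**The case against.** - **No error is shown.** An unadjusted comparison is valid, and this is a pilot with no power target to miss. That is true, and it is why the point concerns precision only. But a pilot's main product is an estimate with an interval, and section 1.2 still sets a significance criterion.
- **The gain is assumed.** The documents give no ED-15 SD or correlation. Against follow-up scores, power moves only from 48% to 50% at r = 0.3. This stands, and the result has to be given as a range. The 64% and 71% figures rest on strata effects for which the documents offer no evidence.
- **Weak prediction is not enough in every setting.** With allocation not blocked within strata, the three-covariate model breaks even with follow-up scores at |r| of about 0.23 for 60 participants. With strata balanced across arms, it is already slightly narrower at r = 0.2 (0.511 against 0.515). The table therefore errs toward understating the benefit.
- **Section 8.3 has larger gaps.** It names no primary time point and no handling of missing data, and data from withdrawn participants stop at withdrawal. Those are separate issues that adjustment does not solve, and the adjustment does not depend on them.
- **Some details need settling.** The diagnosis wording in 7.3.3 can be split into two levels in more than one way. The child-program survey list in 7.2 (Study Procedures) omits EDE-Q, although the 7.1 schedule includes it at enrollment. The first needs a definition; the second affects a secondary score only.

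**Conclusion.** The concern holds. Section 8.3 makes neither enrollment ED-15 nor the randomization strata a covariate, although both are already recorded. With 30 per arm, r between 0.3 and 0.7 and strata of no effect, specifying all three covariates narrows the 95% interval by 2% to 27% against follow-up scores and by 17% to 5% against change scores. At r = 0.5 and a 0.5 SD difference, power is about 58% instead of 48%. The worst case considered, with nothing prognostic, costs about 2 points of power, or about 1 point if the arms are balanced within strata. Most of the gain comes from enrollment ED-15; the stratum terms add precision only if age or diagnosis predicts outcome beyond baseline. The size depends on a correlation the documents do not give, so confidence in the magnitude is medium. The change should be made, but the plan is not invalid without it.

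**What to change.** State in section 8.3 that ED-15 at 3 weeks, 6 weeks and 6 months is compared between arms by ANCOVA, with arm, enrollment ED-15, age stratum and diagnosis stratum as main effects, reporting the adjusted difference and its 95% interval. Use the same form for the other continuous scores, each with its own enrollment value. Define the two diagnosis levels as they are coded for randomization.

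The cost for ED-15 is wording only: no new visit, form or participant. The model uses three more degrees of freedom, leaving 55 residual instead of 58 with 60 complete participants, or 45 instead of 48 with 50.

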3.3 Early Withdrawal of Subjects

3.3.1 Criteria for removal from study

Insert subject withdrawal criteria (e.g., safety reasons, failure of subject to adhere to protocol requirements, subject consent withdrawal, disease progression, etc.).

- New need for medical hospitalization for malnutrition or eating disorder
- Need for escalation of level of care for eating disorder, that is, requirement for inpatient or residential-level eating disorder care
- New need for opioid painkillers
- Subject consent withdrawal
- Inability to adhere to protocol requirements
- New diagnosis of pregnancy
- New elevation of three times the upper limit of normal for age in either alanine aminotransferase (ALT) or asparagine aminotransferase (AST).

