The subject will be provided with oral naltrexone or placebo weekly from the MSHMC research pharmacy. Subjects will be given one weeks' worth of medication at a time. Subjects will be randomized at enrollment to receive either study drug (naltrexone) or placebo. Participants or parents of minor participants will be provided study drug or placebo following completion of urine drug screen and consent/assent. Patients will take the medication daily while they are in programming; after completion of programming or withdrawal from the study they will no longer be given study medication. For subjects who are enrolled in child PHP and who eat meals with parents, the families may choose to administer study drug during meals at programming. For adult patients enrolled in adult programming, subjects may choose to self-administer the medication.

On their first contact with PHP, all patients in Adult PHP complete various eating disorder indices as a part of routine care, including the ED-15, PHQ-9, GAD-7, and EDE-Q. This battery of indices is repeated every 3 weeks while a patient is in programming.

For those who are enrolled in this study, they will complete their routine indices, in addition they will also complete the BIS/BAS and the ABUSI at enrollment and at weeks 1, 3, and 6 while enrolled in the study. Participants will also be asked to take the routine indices (ED-15, EDE-Q, PHQ, GAD, BIS/BAS, and ABUSI) at week 8 or 9 for a post-treatment evaluation. These will be taken in an in-person medical appointment or electronically via RedCap

6 months after enrollment, subjects will be sent copies of ED-15, EDE-Q, PHQ, GAD, BIS/BAS, and ABUSI indices either in an in-person medical appointment or via RedCap to complete. If the patient returns for medical follow-up between 5 and 7 months after enrollment, their height, weight, and body mass index will also be recorded to determine if weight restoration was maintained.

Patients in Child PHP typically complete a different inventory every three weeks as part of routine care. If a patient choses to participate in this study they will be asked to complete the same surveys as participants in Adult PHP (ED-15, GAD-7, and PHQ-9), and they will receive the same amount and type of compensation as those who already take them as part of standard of care.

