7.1.2 Visit 2 or Day 2 or Post-test, etc. (If applicable)

Provide a description of what procedures will be performed on visit 2 or day 2 or post-test in order of how these will be done. If your study involves more than two sessions or visits replicate this section for each additional session or visit (e.g., 7.2.3, 7.2.4, etc.).

On the first day of study participation after enrollment, all subjects will receive a complete set of vital signs (including heart rate, blood pressure, respiratory rate, temperature, and weight) and urine drug screen including screening for opioid substances prior to receipt of their first dose of study article.

Routine care during PHP for any participant includes every-other-week in-person medical exams for the duration of the patient's stay in program, as well as frequent appointments following completion of PHP, until discharge from clinic. At each medical appointment, patients receive a comprehensive physical exam including complete vital signs as above, and are routinely asked about mood changes, physical changes, difficulty or ease of adhering to routine program protocols, etc. All patients participating in PHP complete routine surveys to assess eating disorder recovery at intake and every three weeks until completion of program. For participants in this study, the documentation of their three- and six-week appointments will be reviewed for evidence of adverse effects related to study participation by study personnel. Participants will also complete two additional surveys, the ABUSI and BIS/BAS, beyond their routine PHP surveys at weeks three, six, and eight/nine. Routine medical testing will be obtained according to clinical need at all medical visits, regardless of participation in this study, for all patients participating in PHP.

For patients participating in this study, liver function panel will be obtained once every 3 weeks at no cost to study participants for the purpose of monitoring drug safety, as well as completion of all of the relevant study indices

The vast majority of patients who require PHP have a routine medical follow-up at approximately six months; for those who do not this appointment will be made at no cost to the participant. At this appointment, participants will again undergo a comprehensive physical

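### The comparison is worded by drug received, and nothing says participants are analysed in the arm to which they were randomized

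*Combined protocol and SAP*

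**What the plan says.** The analysis section defines the groups once: "data will be analyzed for differences between participants receiving naltrexone and participants receiving placebo" (8.3). The primary outcome is a "clinically and statistically significant reduction in ED-15 score in those receiving medication vs placebo" (1.2), and the hypothesis in 1.1 contrasts patients on naltrexone with patients on placebo in the same receipt terms. No section defines an analysis population, gives an intention-to-treat rule, or says how to count people who are randomized but not dosed, who stop, or who adhere poorly.

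Elsewhere the protocol separates assignment from receipt:

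- **Randomization.** "Subjects will be randomized at enrollment using RedCap" (7.3.3).
- **Dispensing.** Participants or parents "will be provided study drug or placebo following completion of urine drug screen and consent/assent" (7.2 Study Procedures). Section 7.1.2 adds a "urine drug screen including screening for opioid substances prior to receipt of their first dose of study article".
- **Removal.** Section 3.3.1 lists escalation of care, new opioid need, pregnancy, raised transaminases and "Inability to adhere to protocol requirements". Sections 9.8 and 18.7 stop study article on raised AST/ALT. Sections 10.0 and 19.1.2 withdraw participants for severe effects or for harm probably related to study article.
- **Data after removal.** Section 3.3.2 uses a withdrawn participant's data only up to withdrawal.
- **Later treatment.** Study drug is limited to six weeks (7.2 Duration of Participation; 7.3.2), while 8.3 also compares outcomes at 6 months. Section 7.3.2 offers open-label naltrexone to participants who report benefit that was lost when study article stopped, and does not make arm a condition.

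**The concern.** Randomization protects the comparison only if people are counted in the arm drawn for them. If the groups are those who received each capsule, membership can depend on events after randomization. The protocol provides several such events, and some of them (mood change, nausea, transaminase elevation) are on its own list of naltrexone risks in section 10.0. Pill counts are collected (7.3.4), so a grouping by receipt could also be built after the data have been seen.

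The stake is the primary efficacy claim. With 30 people per arm, leaving out a few can move the estimate noticeably, and a reader could not tell from the plan whether leaving them out was intended.

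**Working it through.** **Does the text fix the grouping?** There is no plan figure to reproduce here. The sample size is 30 + 30 = 60, chosen for feasibility, with no alpha, power, SD or dropout rate stated (8.1, 8.2). The first check is therefore textual, by type of participant and time point.

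1. *Randomized, never dosed.* Randomization is at enrollment, and capsules follow a drug screen with a further screen before the first dose. Section 7.1.1 lets enrollment labs for psychiatry-visit enrollees come up to seven days later. Sections 4.2.4 and 6.2.3 place the negative screen before enrollment, which narrows this route but does not close it. Such a person received neither product, so the literal wording puts them in neither group.
2. *Dosed, then stopped.* This person did receive the capsule, so the wording of 8.3 alone does not exclude them. Their week-6 or 6-month score is lost through 3.3.1 and 3.3.2.
3. *Six months.* Nobody is still on study drug under 7.3.2. Current receipt could only mean open-label use, which follows perceived benefit and is not limited to one arm. Section 7.3.2 ties the offer to completing the study and does not settle whether it can precede the 6-month comparison.
4. *Week 6 for early completers.* Sections 7.2 Study Procedures and 9.2 end study drug with programming, whereas 7.3.2 continues it to six weeks. These sections must be reconciled. Until then, who is receiving drug at week 6 is itself unclear.

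The assigned arm is the only grouping defined for everyone at every time point.

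**How large could the effect be?** This is an illustration only. The 30 per arm comes from 8.1. Everything else is assumed: no true effect, unit SD, *k* people dropped from one arm and none from the other, and those people scoring *g* SD worse than the rest. Comparable people remain counted in the other arm.

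- Bias = (k/30) × g.
- Standard error = √(1/(30 − k) + 1/30): 0.265 for k = 3 and 0.274 for k = 6.
- One-sided false-positive rate = 1 − Φ(1.96 − bias/SE).

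| k | g (SD) | Bias (SD) | One-sided false-positive rate |
|---|---|---|---|
| 3 or 6 | 0 | 0 | 2.5% |
| 3 | 0.5 | 0.05 | 3.8% |
| 3 | 1 | 0.10 | 5.7% |
| 6 | 0.5 | 0.10 | 5.5% |
| 6 | 1 | 0.20 | 10.9% |

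A simulation of 20,000 null trials (30 per arm, two-sided 5% t-test) is in line with this. Dropping 20% of one arm, 1 SD worse, gave a bias of 0.20 SD and a two-sided error of 10.2%. The simulation lets the worse-scoring people widen the spread of the arm that keeps them, which the formula does not. Analysis by assignment with complete outcomes gave 4.7% to 5.2% in every scenario. If both arms lose the same *k* with the same *g*, the two shifts cancel and the bias is zero.

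**The case against.** The best defence is that *receiving* simply means the arm. Section 7.2 Study Procedures says "Subjects will be randomized at enrollment to receive either study drug (naltrexone) or placebo", which runs assignment and receipt together. Section 7.3.2 speaks of being randomized to the medication group, and 8.3 itself compares the two groups at baseline, before anyone has taken a dose. This is a fair reading and may be what was meant. It stands as a reason not to say that the plan announces an as-treated analysis. It does not remove the gap, because no section says so.

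A reader might infer three stronger things that the documents do not support:

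- *That participants switch groups.* No crossover is planned in the six treatment weeks, and current naltrexone use is an exclusion (3.2). The only visible route is the open-label offer, which could matter at 6 months but not at weeks 3 or 6.
- *That the wording favours naltrexone.* Failed screens before the first dose cannot be caused by a blinded capsule and should be roughly balanced. Tolerability exits may fall more on naltrexone, but section 10.0 lets minor to moderate effects continue, and nothing links such exits to worse ED-15 scores. Removal for escalation of care could take poor responders mainly from placebo and bias against the drug.
- *That one sentence in 8.3 cures the problem.* It does not recover scores that were never collected after withdrawal.

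**Conclusion.** The point holds as a gap in the definition of the comparison: the groups are worded by receipt in 1.1, 1.2 and 8.3, and no section restores analysis by randomized arm. On a literal reading never-dosed people can be left out and the 6-month comparison has no usable groups. Combined with 3.3.2, later outcomes of people who stop are lost.

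The illustrated range of 0 to 0.20 SD, with a one-sided false-positive rate of 2.5% to about 11%, rests on assumed numbers of people dropped, loss from one arm only, and an assumed deficit in their scores. The documents supply none of these, so neither the size nor the direction of bias is established. Severity: SHOULD-FIX.

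**What to change.** 1. **Section 8.3, with matching wording in 1.1 and 1.2.** State that the primary comparison includes every randomized participant, grouped by randomized arm whatever doses were taken, at each time point including 6 months.
2. **Section 3.3.2.** Separate stopping study article from withdrawing consent. Participants who stop but have not withdrawn consent should still be sent the planned ED-15 surveys through REDCap. Section 7.3.2 already plans remote surveys for those who finish the program early, so the mechanism exists.
3. **Comparison by doses taken.** Keep any such analysis, based on pill counts, as a sensitivity analysis.

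The cost is a few sentences and some extra survey follow-up. If adherence is poor, the estimate by assigned arm will be smaller than the one by doses taken. If the assigned arm was always intended, item 1 only records it. It should be recorded before unblinding to be credible.
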